Following randomization on Day 1, subjects will receive either a single IV dose of 3600 mg of ASN100 (comprised of separate infusions each of 1800 mg ASN-1 and 1800 mg ASN-2) or matching placebos, per their assigned randomization scheme.

If, as part of routine standard of care, additional respiratory and/or other microbiological specimens are collected for culture during the study, results will be documented within the electronic Case Report Form (eCRF). As fully described within the study laboratory manual, bacterial isolates recovered from these specimens that are deemed pathogens by the Investigator (if retained and available at the study site local microbiology laboratory) will be sent to a central microbiology laboratory for confirmation of pathogen identification (all isolates) and susceptibility testing (*S. aureus* isolates only).

NOTE: Subjects who are heavily colonized and who would have otherwise qualified for randomization, but who are found to have already progressed to pneumonia, may be eligible to enroll in a site-specific pilot treatment sub-study. See [Appendix C](#) for criteria.

Randomized subjects will be monitored daily for the signs and symptoms of pneumonia (see Section 7.4.2 and [Table 1](#)) and other *S. aureus*-associated infections while hospitalized up to Day 21.

All randomized subjects will undergo a study visit on Day 22 (+2 days). A follow-up visit will occur on Day 28 (+2 days) to assess mortality. This visit may be conducted via telephone if the subject is no longer hospitalized.

For subjects who remain hospitalized between Day 40 and Day 90 at the institution where they receive study treatment, a follow-up safety visit will be performed on the day of discharge.

All randomized subjects will return for a Safety Visit on Day 90 ( $\pm 7$  days) (if the subject is unable to return to the site, this visit may be conducted by telephone). Subjects who discontinue the study prior to Day 22 will undergo an Early Termination Visit. The end of the study will occur upon completion of the last Day 90 visit by the last subject.

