## 6.6 Follow-Up Period

### 6.6.1 Day 28 (+2 Days) Follow-Up

The following procedures will occur during a follow-up telephone call or visit, if the subject remains hospitalized, on Day 28 (+2 days):

- Assess ventilator device status (if applicable); and
- Assess for survival and discharge disposition.

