### 6.6.3 Safety Visit (Day 90 [ $\pm 7$ Days])

The following procedures will be performed at the Safety Visit on Day 90 ( $\pm 7$  days). If the subject is unable to return to the site, this visit may be conducted by telephone, with procedures performed as appropriate (i.e., concomitant medications and adverse events collected):

- Perform limited physical examination (to include, at a minimum, a pulmonary examination [including auscultation]);
- Obtain vital sign measurements, including oxygenation status;

- Assess ventilator device status (if applicable);
- Obtain a blood sample for ADAs;
- Perform 12-lead ECG;
- Assess for survival and discharge disposition;
- Obtain a blood sample for PK measurement and assessment of anti-*S. aureus* toxin antibodies;
- Track days on ventilator from randomization;
- Track days in ICU (or other observation area) from randomization;
- Record concomitant medications; and
- Perform adverse event assessment.

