**Table 2. Definition of Hospital-Acquired and Ventilator-Associated Bacterial Pneumonia**

Indication	Definition
HABP	
 
• A chest X-ray showing new or progressive infiltrates suggestive of pneumonia (as assessed by the Investigator);
 
• At least ONE of the following:               
 
○ Has been hospitalized for >48 hours, or
 
○ Developed clinical signs and symptoms within 7 days following hospital discharge;
 
 
 
• At least ONE of the following:               
 
○ New onset or worsening pulmonary signs/symptoms such as cough, dyspnea, tachypnea (e.g., respiratory rate >25 breaths per minute), expectorated sputum production, or the requirement for mechanical ventilation (if subject is not already ventilated);
 
○ Need for acute changes in ventilator support to enhance oxygenation or to the amount of PEEP; or
 
○ New onset of suctioned respiratory secretions; AND
 
 
 
• At least ONE of the following clinical signs/symptoms:               
 
○ Temperature >38°C or <35°C,
 
○ WBC count ≥10,000 cell/mm^3 or ≤4500 cell/mm^3, or
 
○ >15% immature neutrophils (bands) on peripheral blood smear.
 
 
 

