### 10.2.6 Sample Size Determination

The estimated incidence of progression to *S. aureus* pneumonia in mechanically ventilated subjects with heavy colonization is approximately 25% within 22 days of randomization.

Assuming a 2-sided significance level of 0.05 and a desired power of 80% to detect a significant difference between *S. aureus* pneumonia incidence rates of 25% in the placebo group and 12.5% in the ASN100 treatment group (50% reduction), 152 evaluable subjects are required in each treatment group. A sample size of 304 subjects (152 subjects per treatment group) will yield 80% power to detect a 50% reduction in the incidence of *S. aureus* pneumonia with ASN100 treatment when assuming a 25% incidence rate of *S. aureus* pneumonia in placebo-treated subjects. Assuming a 14% non-evaluable rate, approximately 354 subjects (177 subjects per treatment

group) will be randomized. Assuming the screen failure rate is about 84%, approximately 2250 subjects will be screened.

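### A discharged subject who cannot attend Day 22 has no scheduled pneumonia assessment from discharge to Day 21, because Day 22 has no telephone fallback

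*Protocol*

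**What the plan says.** **Window.** Protocol 7.1 and SAP 5.2.4 count *S. aureus* pneumonia up to but not including Day 22.

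**In hospital.** Protocol 3.2 has subjects monitored daily for pneumonia "while hospitalized up to Day 21". Protocol 6.5.2, note c of Appendix A and SAP 4.2 carry the same restriction.

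**Day 22.** Protocol 3.2: "All randomized subjects will undergo a study visit on Day 22 (+2 days"). Section 6.5.3 includes assessment of pneumonia signs and symptoms, and SAP 4.2 calls this the visit for evaluating efficacy. Out-patients are expected, since the physical examination is limited to those in hospital. No telephone alternative is given.

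**Later contacts.** Protocol 6.6.1: "The following procedures will occur during a follow-up telephone call or visit, if the subject remains hospitalized, on Day 28". It covers ventilator status, survival and discharge disposition only. For a subject who cannot return on Day 90, Protocol 6.6.3 says "this visit may be conducted by telephone, with procedures performed as appropriate", meaning concomitant medications and adverse events.

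**Endpoint after discharge.** The HABP definition in Protocol Table 2 admits a subject who "Developed clinical signs and symptoms within 7 days following hospital discharge".

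**Analysis.** SAP 5.2.2 assigns Indeterminate when data do not allow Yes or No. SAP 7.11.1 divides events by all subjects in the arm and treats those discontinued before Day 22 as non-events.

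**The concern.** The endpoint extends past discharge, but scheduled surveillance does not. Take a subject discharged on Day 10 who cannot travel on Day 22. The next scheduled contact is the Day 28 call, which does not ask about pneumonia. Under Protocol 9.1, pneumonia meeting the study definition is in general not recorded as an adverse event. An episode managed elsewhere without admission might therefore come to light only through the Day 90 medication review, more than two months after the window closes.

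At stake is the completeness of the primary endpoint. Events missed equally in both arms lower both rates, shrink the absolute difference and cost power. The SAP does not clearly cover this subject, who has not plainly discontinued from the study, so the sensitivity analysis that counts discontinuation as an event may not apply. If the subject is left Indeterminate, the all-subjects denominator makes that a non-event in effect, and the SAP specifies no analysis that counts Indeterminate as an event.

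**Working it through.** **1. The plan's own figure.** Protocol 10.2.6: "Assuming a 2-sided significance level of 0.05 and a desired power of 80"%, with "incidence rates of 25% in the placebo group and 12.5% in the ASN100 treatment group (50% reduction"). For two proportions with pooled variance and no continuity correction:

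n = [1.960 × √(2 × 0.1875 × 0.8125) + 0.8416 × √(0.25 × 0.75 + 0.125 × 0.875)]² / 0.125² = (1.0819 + 0.4586)² / 0.015625 = 151.9, so 152.

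This matches "152 evaluable subjects are required in each treatment group". Power at 152 per arm is 80.0%, and 152/0.86 gives 177 per arm, or 354. The sample size is not in dispute.

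**2. Share of events after departure.** The documents give no discharge rate or post-discharge hazard, so these inputs are assumptions: a fraction d leaves at about Day 12, leaving 9 of 21 days outside daily monitoring, with hazard after leaving r times the in-hospital hazard.

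Share = 9dr / (21 − 9d + 9dr)

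| d | r = 0.25 | r = 0.5 | r = 1 |
|---|---|---|---|
| 20% | 2.3% | 4.5% | 8.6% |
| 30% | 3.6% | 6.9% | 12.9% |
| 40% | 4.9% | 9.4% | 17.1% |

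For d = 30%, r = 1: 2.7/21 = 12.9%. For r = 0.25: 0.675/18.975 = 3.6%.

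**3. Upper bound.** If every such event were missed at d = 30%, 25% v 12.5% would be observed as 24.1% v 12.1% (r = 0.25) to 21.8% v 10.9% (r = 1). Power at 152 per arm would be 78.2% to 73.1%. This overstates the loss, because leavers who attend Day 22 are assessed.

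**4. Adding the missed visit.** Only leavers who miss Day 22 lose scheduled ascertainment. If 1 in 5 does (also an assumption), the share missed is 3.6%/5 = 0.7% to 12.9%/5 = 2.6%. Observed rates become 24.8% v 12.4% to 24.4% v 12.2%, and power 79.7% to 78.8%.

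**5. Post-discharge onset limited to 7 days.** If only the first 7 days after discharge count, in line with the HABP clause, the share at d = 30% is 2.1/20.4 = 10.3% (r = 1) or 0.525/18.825 = 2.8% (r = 0.25). One fifth of that is 2.1% or 0.6%.

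**The case against.** **Other routes exist.** An overnight admission meets the SAE definition (Protocol 9.2), and SAEs are reportable to Day 90 wherever the subject is (9.3). Protocol 9.1 keeps SAE reporting for pneumonia that is serious, and requires new pulmonary symptoms short of the definition to be recorded as adverse events. Medications are recorded throughout (5.7.2). The SAP plans a subgroup on readmission within 30 days (7.12) and analyses of pneumonia to Day 90 (7.11.2), which presuppose post-discharge data. This stands: a reader might infer that post-discharge pneumonia cannot be detected at all, and the documents do not support that. But these routes are passive. They depend on the site hearing of the episode, and nothing in the documents requires retrieval of the imaging and culture results that SDO1 needs.

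**The analysis handles unobserved time.** The Kaplan-Meier analyses censor event-free and Indeterminate subjects, using the last assessment without pneumonia (SAP 7.3.2, 7.11.2). This stands in part. Censoring adjusts for shorter observation in a supporting analysis. It does not recover a missed event, and the primary analysis does not use it.

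**Other visits.** The Early Termination visit (6.7) also lacks a telephone option, so Day 22 is not unique in that. It serves withdrawn subjects, however, not those still in the study. Protocol 8.2.1 asks for a Day 14 PK sample from all subjects, while 6.5.2 lists it among in-hospital procedures. Even if drawn after discharge, no pneumonia assessment is attached to it.

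**Transfer.** A reader might infer that monitoring ends when a subject moves to another hospital. The documents do not say so. A limit to the treating institution appears only for the Day 40 to Day 90 discharge visit.

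**Unseen documents.** The Population and Outcome Plan or the eCRF instructions may already require outside records. That cannot be checked here.

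**Conclusion.** The point holds in a limited form. A discharged subject who remains in the study and cannot attend Day 22 has no scheduled pneumonia ascertainment from discharge to Day 21, and in effect counts as a non-event in the primary analysis.

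The probable size is small: about 0.7% to 2.6% of events and roughly one percentage point of power, assuming 30% leave at about Day 12, a relative hazard of 0.25 to 1, and 1 in 5 leavers missing Day 22. The 3.6% to 12.9% range is a ceiling. Reading it as the expected loss would require every leaver to go unassessed, which 6.5.3 contradicts. These figures also assume that no missed case comes in through the passive routes.

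Two further readings are not supported. One is bias between the arms: that would need discharge or attendance to differ by treatment, and the documents give no evidence of it. The other is automatic loss from the PP Population: SAP 5.1.3 leaves adequacy of assessments to medical review of available data.

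This is a minor improvement to ascertainment. It does not challenge the design or the sample size.

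**What to change.** - In Protocol 3.2 and 6.5.3, keep the in-person Day 22 visit as the default, but allow a telephone contact when a discharged subject cannot attend. Use the Day 28 call (6.6.1) as a fallback if that contact fails.
- In that contact, ask about pneumonia diagnosis, chest imaging, respiratory cultures, new antibiotics and readmission since discharge. For any positive answer, obtain the outside records so that SDO1 can be assigned by event date.
- State whether daily monitoring continues after transfer to another hospital and, if so, how the data are obtained.

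The cost is protocol wording, a few eCRF fields, one fallback call per affected subject and a small number of record requests. A call cannot supply the Day 22 blood samples, ECG, imaging or respiratory specimen, so it should be used only where the visit would otherwise be missed. Treatment, eligibility and sample size do not change.

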### **3.3 Study Indication**

The prevention of *S. aureus* pneumonia in mechanically ventilated subjects who are heavily colonized with *S. aureus*.

## 4 SELECTION AND WITHDRAWAL OF SUBJECTS

### 4.1 Inclusion Criteria

Subjects must meet all of the following criteria at the Screening and Randomization Visits in order to be eligible for randomization into the study:

1. Subject, legally authorized representative (LAR), or CIP (if applicable) has provided written informed consent;
2. Subject is  $\geq 18$  years of age at the time of enrollment;
3. Subject is currently hospitalized and is mechanically ventilated endotracheally (i.e., orotracheal or nasotracheal) and, in the Investigator's opinion, will require ongoing ventilator support for at least 48 hours;

NOTE: Subjects with a tracheostomy at the time of enrollment are not eligible. After enrollment, conversion to tracheostomy is permitted per standard of care.

4. Female subjects must not be pregnant or lactating. Female subjects of childbearing potential must have a documented negative pregnancy test at the Screening Visit. Female subjects may be enrolled on the basis of a negative urine pregnancy test, pending the result of a negative serum pregnancy test prior to randomization; and
5. Female subjects of childbearing potential and non-surgically sterile male subjects who are sexually active must agree to use an approved highly effective form of contraception from the time of informed consent until 165 days post-dose. Approved forms of contraception include hormonal intrauterine devices, hormonal contraceptives (oral birth control pill, depo, patch, or injectable) together with supplementary double barrier methods such as condoms or diaphragms with spermicidal gel or foam.

NOTE: The following categories define women who are NOT considered to be of childbearing potential:

- Premenopausal female with 1 of the following:
  - Documented hysterectomy,
  - Documented bilateral salpingectomy, or
  - Documented bilateral oophorectomy, or
- Postmenopausal female, defined as having amenorrhea for at least 12 months without an alternative medical cause.

### 4.2 Exclusion Criteria

Subjects who meet any of the following criteria at the Screening and/or Randomization Visit will be excluded from participation in the study:

1. Subject has received IV immunoglobulin therapy within 4 months prior to the Screening Visit;
2. Subject has a chest X-ray or thoracic CT scan that is definitive for a diagnosis of pneumonia;

3. Subject demonstrates both of the following:
  - a. Need for acute changes in ventilator support to enhance oxygenation or to the amount of positive end-expiratory pressure; AND  
NOTE: Changes made in ventilator support due to day-to-day maintenance other than those changes made to improve oxygenation will not exclude a subject from participation in the study.
  - b. New onset of purulent suctioned respiratory secretions;
4. Subject has a known and documented ETA culture showing heavy colonization with a Gram-negative organism at enrollment or at any time during the Screening period;  
NOTE: Randomization should not be delayed while waiting for Gram-negative results if heavy colonization with *S. aureus* has been confirmed.
5. Subject has been diagnosed with neutropenia (absolute neutrophil count <500/mm^3);
6. Subject has a severe non-pulmonary source of infection which, in the Investigator's opinion, would interfere with the conduct of the study or jeopardize the subject's safety;
7. Subject is currently on either continuous veno-venous hemodialysis or extracorporeal membrane oxygenation;
8. Subject has been previously exposed to ASN100 or ASN-1 or ASN-2, individually;
9. Subject has a known hypersensitivity to ASN100 or any of its excipients;
10. Subject has received any investigational product within 30 days prior to the Screening Visit (or 5 half-lives of the investigational product, whichever is longer);
11. Subject has, in the opinion of the Investigator, a high probability of death within 72 hours of enrollment;
12. Subject is, in the opinion of the Investigator, not able or willing to comply with the protocol;
13. Any condition that, in the opinion of the Investigator, would compromise the safety of the subject, the potential activity of the study drug, or the quality of the data; or
14. Subjects with a known history or current (suspected) diagnosis of cytokine release syndrome associated with the administration of peptides, proteins, and/or antibodies.

NOTE: Subjects with a prior history of sepsis are not excluded.

#### **4.3 Randomization Criteria**

Following the Screening Visit, eligible subjects who meet all of the inclusion criteria and none of the exclusion criteria will be screened daily (while mechanically ventilated) for up to 8 days via quantitative or semi-quantitative culture of an ETA to identify those subjects who are heavily colonized with *S. aureus* (see Section 3.1).

Screening for heavy *S. aureus* colonization by ETA culture will continue on Day 11 and Day 14 provided the subject remains mechanically ventilated, for a total Screening Period of up to 14 days. Additional ETA screening may occur on Days 9, 10, 12, and 13 at the discretion of the Investigator and providing the subject remains mechanically ventilated.

Once an enrolled subject has an ETA culture reported positive for heavy *S. aureus* colonization and meets all of the inclusion and none of the exclusion criteria, they are eligible for randomization. If they are not randomized on this occasion according to the protocol, they are no longer eligible for continued ETA sampling and randomization, and will be discontinued from the study; however, if subjects are extubated and subsequently re-intubated/mechanically ventilated, they are eligible for re-screening as a new subject enrollment. Subjects who were previously randomized are not eligible to be re-consented and re-screened.

At the time of randomization, if a subject's screening ETA culture also shows heavy colonization of a Gram-negative organism (i.e., heavy co-colonization of both Gram-positive and Gram-negative organisms), the subject will not be randomized into the study.

NOTE: Randomization should not be delayed while waiting for Gram-negative results if heavy colonization with *S. aureus* has been confirmed.

At the Randomization Visit, subjects must meet all of the following requirements to be randomized into the study:

1. Subject continues to meet all of the inclusion criteria and none of the exclusion criteria required at the Screening Visit;

NOTE: Subjects who undergo tracheostomy after enrollment are still eligible for randomization, provided they remain mechanically ventilated (see criterion 3 below).

2. Subject is heavily colonized with *S. aureus* as determined by either quantitative or semi-quantitative culture of an ETA (see Section 3.1);

NOTE: The results of the qualifying ETA culture must allow randomization to occur within 48 hours (or up to 60 hours with Medical Monitor approval) from the time the ETA sample was collected. Subjects with ETA culture results obtained after 60 hours showing heavy colonization of *S. aureus* may not be randomized and will be discontinued from the study.

3. Subject remains mechanically ventilated and, in the Investigator's opinion, will require ongoing ventilator support for at least 48 hours; and
4. Subject has, in the opinion of the Investigator, a probability of survival beyond 72 hours post-randomization.

#### **4.4 Withdrawal Criteria**

Participation of a subject in this clinical study may be discontinued for any of the following reasons:

- The subject or LAR withdraws consent from the study for any reason;
- The subject or LAR requests discontinuation from the study for any reason;
- Occurrence of any medical condition or circumstance that exposes the subject to substantial risk and/or does not allow the subject to adhere to the requirements of the protocol;
- Any SAE, clinically significant adverse event, severe laboratory abnormality, intercurrent illness, or other medical condition which indicates to the Investigator that continued participation is not in the best interest of the subject;

- Pregnancy;
- Requirement of prohibited concomitant medication;
- Subject failure to comply with protocol requirements or study-related procedures; or
- Termination of the study by the Sponsor or the regulatory authority.

If a subject withdraws prematurely from the study due to the above criteria (except in the case of withdrawal of consent) or any other reason, study staff should make every effort to complete the full panel of assessments scheduled for the Early Termination Visit. The reason for subject withdrawal must be documented in the eCRF.

In the case of subjects lost to follow-up, attempts to contact the subject must be made and documented in the subject's medical records.

Randomized subjects who are withdrawn will not be replaced.

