## 5 STUDY TREATMENTS

### 5.1 Treatment Groups

Following Screening/Enrollment and upon determination that a subject is heavily colonized with *S. aureus* as determined by a positive quantitative or semi-quantitative culture of an ETA (see Section 3.1), eligible subjects will be randomized in a 1:1 ratio to 1 of 2 treatment groups:

- ASN100 administered either sequentially or simultaneously as 2 separate IV infusions of ASN-1 and ASN-2, or
- Placebo administered either sequentially or simultaneously as 2 separate IV infusions.

Whether ASN-1, ASN-2, or placebo are administered sequentially or simultaneously will be determined by operational considerations of IV access at the time of dosing. If 2 IV lines are available for simultaneous administration this is preferable; however, if IV access or other considerations support sequential administration, this is allowed provided that both infusions are completed within 3 hours.

Following randomization on Day 1, subjects will receive either a single IV dose of 3600 mg of ASN100 (comprised of separate infusions each of 1800 mg ASN-1 and 1800 mg ASN-2) or matching placebos, per their assigned randomization scheme.

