### **5.7 Prior and Concomitant Medications and/or Procedures**

#### 5.7.1 Excluded Medications and/or Procedures

The use of any investigational product within 30 days prior to the Screening Visit (or 5 half-lives of the investigational product, whichever is longer) is prohibited. Any immunoglobulin preparation for any medical indication is prohibited through follow-up Day 90 of the study.

Prior use of ASN100, ASN-1, or ASN-2 is prohibited.

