### **6.7 Early Termination Visit and Withdrawal Procedures**

For subjects who are withdrawn from the study prior to Day 22, the following procedures will be performed at an Early Termination Visit:

- Perform limited physical examination (to include, at a minimum, a pulmonary examination [including auscultation]);
- Obtain vital sign measurements, including oxygenation status;
- Perform pregnancy test for female subjects of childbearing potential only;
- Perform clinical laboratory assessments including chemistry, hematology, coagulation, and urinalysis (if clinically indicated);
- Obtain a blood sample for procalcitonin testing;
- Assess ventilator device status (if applicable);
- Obtain adequate respiratory specimen for culture (if clinically indicated);
- Assess for clinical signs/symptoms of pneumonia (Section 7.4.2; Table 1);
- Assess for other *S. aureus*-associated infections;
- Obtain a blood sample for ADAs;
- Perform 12-lead ECG;
- Assess for survival and discharge disposition;
- Obtain a blood sample for PK measurement and assessment of anti-*S. aureus* toxin antibodies;
- Track days on ventilator from randomization;
- Track days in ICU (or other observation area) from randomization;
- Record concomitant medications; and
- Perform adverse event assessment.

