### Follow-Up Reports

The Investigator must continue to follow the subject until the SAE has subsided or until the condition becomes chronic in nature, stabilizes (in the case of persistent impairment), or the subject dies.

Within 24 hours of receipt of follow-up information, the Investigator must update the SAE form electronically in the EDC system for the study and submit any supporting documentation (e.g., subject discharge summary or autopsy reports) to Medpace Clinical Safety via fax or email. If it is not possible to access the EDC system, refer to the procedures outlined above for initial reporting of SAEs.

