7.11.3. Secondary Efficacy Endpoints

Duration of mechanical ventilation and length of hospital ICU stay during the first 21 days post-randomization will be summarized descriptively and compared between treatment groups using a Wilcoxon rank sum test in the MITT, ITT, and PP Populations.

The other secondary endpoint, 28-day all-cause mortality in the ITT, MITT and PP Population, will be descriptively summarized by treatment group. All-cause mortality rate at Day 28 based on Kaplan-Meier estimates along with the 95% confidence interval will also be presented for each treatment group. Subjects whose survival status are unknown

due to early termination or who are lost to follow up will be censored at the last day the subject was known to be alive.

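### Protocol 4.4 does not separate stopping study drug or procedures from leaving the study, so a dosed subject can be withdrawn for a medical event with no planned pneumonia, Day 28 or Day 90 follow-up

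*Protocol*

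**What the plan says.** **Dosing.** Protocol 5.1: "Following randomization on Day 1, subjects will receive either a single IV dose of 3600 mg of ASN100" or matching placebo. No further dose is planned. Protocol 5.6.3 has its own rule for stopping an infusion.

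**Withdrawal.** Protocol 4.4 opens "Participation of a subject in this clinical study may be discontinued for any of the following reasons". What it ends is participation in the study, not treatment. Its grounds include "Any SAE, clinically significant adverse event, severe laboratory abnormality, intercurrent illness, or other medical condition which indicates to the Investigator" that staying in the study is not in the subject's interest. They also include pregnancy, non-compliance and "Requirement of prohibited concomitant medication". The last can arise after dosing, because Protocol 5.7.1 states: "Any immunoglobulin preparation for any medical indication is prohibited through follow-up Day 90 of the study". Withdrawn randomized subjects are not replaced.

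**What follows withdrawal.** Protocol 6.7: "For subjects who are withdrawn from the study prior to Day 22, the following procedures will be performed at an Early Termination Visit". Protocol 3.2 schedules Day 22 and Day 90 visits for all randomized subjects, but in the same paragraph sends those who discontinue before Day 22 to the Early Termination Visit. Under Protocol 9.1, adverse events are collected only while participation lasts. Two duties go further. In Protocol 9.3, "The Investigator must continue to follow the subject until the SAE has subsided" or reaches another stated end point, and Protocol 9.4 has pregnancies followed to completion.

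**Analysis.** SAP 7.3.2 and 7.11.1 count a subject who discontinues before Day 22, for any cause, as not having *S. aureus* pneumonia. For 28-day mortality, SAP 7.11.3 says that subjects of unknown survival status "due to early termination or who are lost to follow up will be censored at the last day the subject was known to be alive".

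**The concern.** In a single-dose trial, a dosed subject has no later treatment to stop. What remains is observation, plus study sampling that can be dropped without losing the outcome. Section 4.4 treats the two as one, so a decision to spare a sick subject further procedures also ends planned outcome collection.

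The reasons for leaving are post-randomization illnesses, which may be related to pneumonia, to death and possibly to treatment. Three results are exposed:

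- The primary endpoint, because an unobserved outcome becomes a non-event.
- 28-day mortality, because Kaplan-Meier censoring assumes that leaving is unrelated to prognosis.
- Day 90 safety and immunogenicity, for subjects who may have had the most informative events.

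**Working it through.** **Inputs.** From Protocol 10.2.6 and SAP 6: event rates 25% (placebo) and 12.5% (ASN100), 2-sided 0.05, 80% power, 152 evaluable per arm, 14% non-evaluable, 354 randomized (177 per arm). The withdrawal fraction *w* and the relative risk *k* of withdrawn subjects are assumptions; the documents give neither. The 14% is used as one value of *w* for scale only: it is a non-evaluable rate, not a withdrawal rate.

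**1. The plan's own figures.** With pooled variance and no continuity correction, n = [1.96·√(2 × 0.1875 × 0.8125) + 0.8416·√(0.25 × 0.75 + 0.125 × 0.875)]² / 0.125² = 151.9, so 152 per arm. Power at 152 is 80.0%. 304 / 0.86 = 353.5, so 354. All reproduce.

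**2. Equal withdrawal before any event.** A dosed subject who leaves stays in the MITT denominator and counts as a non-event. Each arm's observed rate is then p × (1 − w·k), and the observed difference is 12.5 × (1 − w·k) points. Power = Φ[(difference − 1.96·SE₀)/SE₁], with SE₀ pooled and SE₁ unpooled, at 177 per arm:

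| w | Difference, k = 1 | Power, k = 1 | Difference, k = 2 | Power, k = 2 |
|---|---|---|---|---|
| 0 | 12.5 | 85.7% | 12.5 | 85.7% |
| 5% | 11.9 | 83.4% | 11.25 | 80.9% |
| 10% | 11.25 | 80.9% | 10.0 | 75.2% |
| 14% | 10.75 | 78.8% | 9.0 | 69.9% |

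Worked cell (w = 14%, k = 2): the rates become 18% and 9%. SE₀ = √(2 × 0.135 × 0.865/177) = 0.0363 and SE₁ = √((0.18 × 0.82 + 0.09 × 0.91)/177) = 0.0360. (0.090 − 0.0712)/0.0360 = 0.522, and Φ(0.522) = 69.9%.

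**3. Withdrawal that differs by arm, no drug effect.** With 25% in both arms, 15% withdrawn on ASN100 and 5% on placebo:

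- k = 1: observed rates 21.25% and 23.75%, a spurious 2.5 points; 2-sided rejection rate 8.7% instead of 5%.
- k = 2: observed rates 17.5% and 22.5%, a spurious 5.0 points; rejection rate 21.7%.

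Equal withdrawal keeps the rate at 5%.

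**4. Mortality.** No figure is given. The documents state neither a mortality rate nor how often status would be unknown.

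**The case against.** **Withdrawal is not compulsory.** The opening of 4.4 is permissive, and the SAE and illness ground needs a best-interest judgement. A reader might infer that any SAE removes the subject and that, SAEs being common in an ICU, many will leave. The text does not support that, and frequency is unknown. Pregnancy, prohibited medication and non-compliance carry no best-interest condition, but they too are permissive.

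**Follow-up does not all stop.** A reader might infer that withdrawal ends all follow-up, or that 4.4 contradicts 9.3 and 9.4. Neither holds. Known SAEs are followed to outcome or death and pregnancies to completion, and these duties can run alongside withdrawal from visits. The Early Termination Visit covers pneumonia signs, survival, ADA, PK and adverse events. SAP 7.11.3 censors only if survival status is unknown. Still, none of this supplies pneumonia status through Day 21 or Day 28 vital status for every withdrawn subject.

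**Withdrawal has uses.** It spares study blood draws and, for volunteers, the sub-study lavage. The list also covers the period of up to 14 days between enrolment and randomization, when pregnancy or intercurrent illness is an ordinary reason not to proceed. Both points stand, and the fix keeps both.

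**The loss may be small, and sensitivity analyses exist.** At average risk and 5% or 10% withdrawn, power at 177 per arm stays above 80%. SAP 7.11.2 includes an analysis that counts discontinuation as an event, and Kaplan-Meier analyses with censoring. These show how much the assumption matters, but they do not recover the true outcome.

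**Conclusion.** The point holds as a design gap whose frequency is unknown. Section 4.4 merges stopping drug or procedures with leaving the study. For a dosed subject withdrawn before Day 22, the plan then collects nothing scheduled beyond one visit, and the SAP turns the gap into a non-event or, where survival status is unknown, possibly informative censoring.

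The size depends wholly on assumed withdrawal. The figures of 11.9, 11.25 and 10.75 points need equal withdrawal, before any event, in subjects of average risk. They are not worst cases: if illness drives withdrawal, risk may be higher, and 14% at double risk gives 9.0 points. Unequal withdrawal is the more serious possibility, because it biases the comparison as well as diluting it.

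The stronger reading, that the rule removes the sickest subjects for no benefit to them, goes further than the documents. The sample size of 152 evaluable per arm and 354 randomized is unaffected. The change is recommended because the loss is avoidable at low cost.

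**What to change.** **Protocol 4.4 and 6.7.** Keep the Investigator's discretion to stop study procedures (sampling, sub-study lavage, on-site visits), and keep the present list for the pre-dose period. Add that a dosed subject who stops procedures remains in follow-up unless consent for follow-up is withdrawn, contact is lost or the study is terminated. For these subjects, collect by chart review or telephone:

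- pneumonia status through Day 21;
- vital status at Day 28;
- safety to Day 90.

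Protocol 3.2 already allows telephone contact at Day 28 for subjects no longer in hospital, and at Day 90 for those unable to return.

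**SAP 7.3.2, 7.11.1 and 7.11.3.** State that data observed after procedures stop are used in the analyses. The non-event rule and the censoring rule would then apply only where status is still unknown.

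**Cost.** A protocol amendment with IRB/IEC approval (Protocol 13.1), possible consent-form wording for continued chart review, and a few chart or telephone contacts. No added subjects and no added procedures for subjects.
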